# 3.2 Secondary objectives

- To evaluate the effect of pasireotide LAR in mean tumor volume variation between baseline and treatment weeks 4, 12, 24, 48, 72, and 96.
- To evaluate the effect of pasireotide LAR in mean percent tumor volume variation between baseline and treatment weeks 4, 12, 24, 48, 72, and 96.
- To evaluate the effect of pasireotide LAR in the proportion of patients reaching tumor volume decrease of at least  $\geq 20\%$  after 4, 12, 48, 72, and 96 weeks of treatment.
- To evaluate the effect of pasireotide LAR on time to tumor response.
- To evaluate the effect of pasireotide LAR on the disease-related symptoms \*
   \* Disease-related symptoms to be evaluated: headache, visual disorders, fatigue, decreased libido, erectile dysfunction (for men only), menstrual irregulative or interruption (only for non-menopausal women).
- To evaluate the effect of pasireotide LAR on the pituitary function on weeks 4, 12, 24, 48, 72, and 96.
- To evaluate the effect of pasireotide LAR on the alpha subunit levels on weeks 4, 12, 24, 48, 72, and 96.
- To evaluate the overall safety and tolerability of pasireotide LAR.
- For the extension phase: duration of response for patients considered as responders (i.e., patients reaching a tumor volume decrease of at least 20% compared to the initial tumor volume).
- To evaluate the percentage of patients remaining with stable tumor volume during the study.

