- 17. Patients with liver disease or history of liver disease, such as cirrhosis, active chronic hepatitis B and C, or persistent chronic hepatitis, or patients with ALT and/or AST > 2 x ULN, total blood bilirubin > 1.5 x ULN, and serum albumin < 0.67 x LLN.
- 18. Patients with blood creatinine > 2.0 x ULN.
- 19. Patients with WBC  $< 3 \times 10^9 / L$ ; Hgb < 90% LLN; PLT  $< 100 \times 10^9 / L$ .
- 20. Patients with any current or previous medical condition that, in the investigator's opinion, might interfere in the study conduction or evaluation of the study results.
- 21. Patients with history of immunological impairment, including positive result for HIV tests (ELISA and Western blot). HIV tests will not be required; however, previous medical history will be analyzed.
- 22. Patients with known hypersensitivity to somatostatin analogues or any other pasireotide LAR compound.
- 23. Patients with active malignant disease within the last five years (except for basal cell carcinoma or in situ cervix carcinoma).
- 24. Patients with presence of uncontrolled, acute suspected, or active chronic infection.
- 25. Pregnant or breastfeeding patients, or patients of childbearing potential who do not adopt a clinically acceptable contraceptive method. If a woman is participating in the study, then one contraceptive method will be sufficient (pill or diaphragm), and the partner must use condoms. If an oral contraceptive is used in addition to condoms, the patient must have adopted this method at least two months prior to enrollment in the study, and must agree to continue to use it throughout the study, and for three months after the end of the study. Sexually active male patients are required to use condoms during the study and for three months after the end of the study, as a precautionary measure (the available data do not suggest any increase in reproductive risk with the study drugs).
- 26. Study participants on the investigational drug 30 days prior to the enrollment visit (Visit 2). Patients must have recovered from all side effects from other investigational therapies.

- 27. Patients with history of non-compliance to medical regimens, or patients considered potentially unsafe, or any circumstance at the time of study enrollment that might prevent the completion of the entire study or the follow-up required.
- 28. Patients with history or recurrence of undue use / abuse of alcohol or drugs within 12 months previous to visit 1 (screening).

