- 29. Presence of Hepatitis B surface antigen (HBsAg).
- 30. Presence of Hepatitis C antibody screen (anti-HCV).
- 31. Patients who had a major surgery / surgical therapy for any cause within 4 weeks before randomization.
- 32. Patients with confirmed hypothyroidism, hypoadrenalism and hypogonadism (except for physiological andropause and menopause), unless appropriately treated with stable doses of hormone replacement therapy for at least 3 months before study entry.
- 33. Patients on growth hormone replacement therapy.
- 34. Patients with uncontrolled cardiovascular, renal or metabolic disorders.
- 35. Patients with severe neurological or psychiatric disorders.
- 36. Patients with contraindications to MRI such as, for example, (but not limited to): brain aneurysm clips, internal wiring of cardiac pacemaker and temporary pacemaker, cochlear implants, hearing devices containing internal non-removable parts, Swan-Ganz catheter, aortic balloon, Endovascular Graft Zenith AAA, and other potential contraindications related to ferromagnetic materials identified in the patient's interview.

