# 7.4.2 Secondary efficacy evaluations

Tumor volume will also be evaluated as described on Section 7.4.1. Time to response will also be obtained (i.e., time to reach tumor volume decrease  $\geq 20\%$ ).

Disease-related symptoms will be reported by patients and recorded by the medical staff, on all Main Phase visits and on visits 13 (week 36), 16 (week 48), 19 (week 60), 22 (week 72), 25 (week 84), and 28 (week 96) of the Extension Phase.

Disease-related symptoms to be evaluated: headache, visual disorders, fatigue, decreased libido. Only for men: erectile dysfunction. Only for non-menopausal women: irregular or interrupted menstrual cycles. The investigator will also ask patients to classify the symptoms above according to a 5-point scale (0 = absent, 1 = mild, 2 = moderate, 3 = severe, 4 = very severe). The remaider will be evaluated as absent or present.

Hormone profiles, including growth hormone (GH), insulin-like growth factor I (IGF-1), follicle-stimulating hormone (FSH), luteinizing hormone (LH), adrenocorticotropic hormone (ACTH), thyroid-stimulating hormone (TSH), prolactin (PRL), cortisol, free T4, and estradiol (for women) or testosterone (for men), will be evaluated in the Screening Period (and will be considered as baseline data) and on Weeks 4, 12, and 24 of the Main Phase. Evaluations in the Extension Phase will be performed on Weeks 48, 72, and 96.

Alpha subunit levels will be measured in the Screening Period (and will be considered as baseline data), on Weeks 4, 12, and 24 in the Main Phase, and on Weeks 48, 72, and 96 in the Extension Phase.

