n(%)	. ,									
Yes										
No										
Total										
Improved, n (%)										
Yes										
95%CI										
No										
Total										

Table 10 (Cont.) – Disease-related symptoms – FAS population

	Total (n=xx)									
	V1	V2	V3	V4	V5	V6	V7	V8	V9	V10
Regular menses ^{c)} ,	n									
(%)										
Yes										
No										
Total										
mproved, n (%)										
Yes										
95%CI										
No										
Total										

a) For each symptom, it will considered as improvement if the severity reduce at least one point (eg. 'Severe' at v₁ and 'moderate' at v₁ will be considered as improvement in vi).

b) For patients who registered 'No' in V₁ and 'Yes' in v_i it will be considered as an improvement in v_i.

c) For patients who registered 'No' in V₁ and 'Yes' in v_i it will be considered as an improvement in v_i.

Table 11 (Cont.) – Alpha-subunit – FAS population

	Total (n=xx)					
	V1	V4	V7	95%CI	V10	95%CI
α subunit (ng/mL)						
N				-		-
Mean				-		-
Median				-		-
Standard Deviation				-		-
Minimum				-		-
Maximum				-		-
Normal				-		-
Abnormal				-		-
CS				-		-
NCS				-		-
Reduction of α subunit ≥50% ^{c)} , n (%)						
Yes						
No						
Total						

CS: Clinically significant; NCS: Not clinically significant. 95%CI: 95% confidence interval.

c) For reduction ≥50%='yes' will be considered all patients who obtained percentage change from baseline in α subunit at visit i' ≥50.

Table 13 – Visual field – FAS population

	Total							
	(n=xx)							
	V1	V2	V4	V5	V7	V8	V9	V10
Right eye								
Normal/abnormal, n (%)								
Normal								
Abnormal								
Mild								
Severe								
Total								
Findings, n (%)								
Upper right quadrantanopia								
Upper left quadrantanopia								
Lower right quadrantanopia								
Lower left quadrantanopia								
Temporal hemianopsia								
Nasal hemianopsia								
Other								
Evolutive information, n (%)								
Stable								
Improved								
Worsened								
Total								
Left eye								
Normal/abnormal, n (%)								
Normal								
Abnormal								
Mild								
Severe								
Total								
Findings, n (%)								
Upper right quadrantanopia								
Upper left quadrantanopia								
Lower right quadrantanopia								
Lower left quadrantanopia								
Temporal hemianopsia								
Nasal hemianopsia								
Other								

Table 13 (Cont.) – Visual field – FAS population

	Total (n=xx)							
	V1	V2	V4	V5	V7	V8	V 9	V10
Left eye Evolutive information, n (%) Stable Improved Worsened Total								

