Mean Median Standard Deviation Minimum			
Maximum			
Normal Abnormal CS			
NCS			
SGPT (U/L) N			
Mean			
Median Standard Deviation			
Minimum Maximum			
Normal Abnormal			
CS NCS			
Alkaline Phosphatase (U/L)			
N Mean			
Median			
Standard Deviation Minimum			
Maximum			
Normal			
Abnormal CS			
NCS			
y-GT (U/L)			
N Mean			
Median			
Standard Deviation Minimum			
Maximum			
Normal			
Abnormal CS			
NCS			
Total bilirubin (mg/dL) N			
Mean			
Median Standard Deviation			
Minimum			
Maximum			
Normal			
Abnormal CS			
NCS			

```
Direct bilirubin (mg/dL)
   Mean
Median
   Standard Deviation
   Minimum
   Maximum
   Normal
   Abnormal
    CS
    NCS
Indirect bilirubin (mg/dL)
   Ν
   Mean
   Median
   Standard Deviation
   Minimum
   Maximum
   Normal
   Abnormal
    CS
    NCS
Albumin (g/dL)
   Ν
   Mean
   Median
   Standard Deviation
   Minimum
   Maximum
   Normal
   Abnormal
    CS
     NCS
```

CS: Clinically significant; NCS: Not clinically significant.

Table B 23 – Hormonal evaluation – Safety population

Table B 23 – Hormonal evaluation – Safe	Total (n=xx)		
	V16	V22	V28
CII (ng/mi)			
GH (ng/mL) N			
Mean Median Standard Deviation			
Minimum Maximum			
Normal Abnormal CS			
NCS			
IGF-I (ng/mL) N			
Mean Median			
Standard Deviation Minimum Maximum			
Normal Abnormal			
CS NCS			
ACTH (pg/mL) N			
Mean Median Standard Deviation			
Minimum Maximum			
Normal Abnormal			
CS NCS			
Cortisol (µg/dl), for patients without intake of g	glucocorticoid		
Mean Median			
Standard Deviation			
Minimum Maximum			
Normal			
Abnormal CS			
NCS			
LH (mUI/mL) N			
Mean Median			
Standard Deviation			
Minimum Maximum			
Normal Abnormal			
CS			
NCS			

```
FSH (mUI/mL)
   Ν
   Mean
   Median
   Standard Deviation
   Minimum
   Maximum
   Normal
   Abnormal
    CS
    NCS
Testosterone (ng/dl)
   Ν
   Mean
   Median
   Standard Deviation
   Minimum
   Maximum
   Normal
   Abnormal
    CS
    NCS
Estradiol (pg/mL)
   Ν
   Mean
   Median
   Standard Deviation
   Minimum
   Maximum
   Normal
   Abnormal
    CS
    NCS
TSH (μUI/mL)
   Ν
   Mean
   Median
   Standard Deviation
   Minimum
   Maximum
   Normal
   Abnormal
    CS
    NCS
Free T4 (ng/dL)
   Ν
   Mean
   Median
   Standard Deviation
   Minimum
   Maximum
   Normal
   Abnormal
    CS
    NCS
Prolactin (ng/mL)
   Ν
   Mean
   Median
```

Standard Deviation
Minimum
Maximum
Normal
Abnormal
CS
NCS

CS: Clinically significant; NCS: Not clinically significant.

Table B 24 – Vital signs – Safety population

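### Menses, LH, FSH and estradiol are tabulated with users and non-users of sex steroids pooled, although entry criteria allow the pill and require replacement in confirmed hypogonadism, so a drug effect can be masked

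*Protocol*

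**What the plan says.** **Entry.** Protocol 5.2, criterion 25, accepts the pill as one of two options: "one contraceptive method will be sufficient (pill or diaphragm), and the partner must use condoms". Where it is an oral contraceptive, "the patient must have adopted this method at least two months prior to enrollment in the study", and she must keep using it throughout the study. Criterion 32 excludes patients with confirmed hypogonadism (physiological menopause and andropause apart) "unless appropriately treated with stable doses of hormone replacement therapy for at least 3 months before study entry".

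**Endpoints.** Protocol 7.4.2 scores the menstrual symptom by sex and menopausal status alone: "Only for non-menopausal women: irregular or interrupted menstrual cycles". Protocol 3.2.1 also lists the incidence of pituitary hormone dysfunction at baseline and at weeks 4 to 96. Neither document defines dysfunction for a patient taking exogenous hormones.

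**Tables.** In SAP Table 10, a woman whose menses are not regular at V1 and are regular at visit i is scored under the rule "it will be considered as an improvement in v_i". Table B 5 repeats the rule for the extension. Tables 30 and B 23 classify LH, FSH and estradiol as normal or abnormal for everyone with a value. In both hormone tables cortisol alone is restricted, with the qualifier "for patients without intake of" glucocorticoid.

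**Partial handling.** SAP Table 4 counts hormone replacement as yes or no. SAP Table 31 compares testosterone, estradiol, TSH and free T4 with and without replacement, at V1 only. Protocol 6.4.3 asks that concurrent medication stay unchanged until the end-of-study evaluations, if possible.

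**The concern.** A woman on the pill or on sex-steroid replacement has a bleeding pattern and gonadal hormone values that largely follow the steroid. That is general pharmacology rather than a figure from the documents, but the SAP accepts the same principle for cortisol. Pooling her with women who take no steroid means that the menses result and the LH, FSH and estradiol counts answer a mixed question.

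Two secondary objectives depend on these rows: the effect on disease-related symptoms and the effect on pituitary function. Protocol 1.1 says that most patients with this tumor have signs and symptoms of hypogonadism, and it names recovery from hypopituitarism as a possible benefit of shrinking the tumor. The study has one arm, so there is no control group against which a steroid effect would cancel.

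**Working it through.** The plan states no figure on this point, so the check is mainly a comparison of passages.

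**1. Is the steroid already present at V1?** Screening (V1) falls at most 28 days before Visit 2. Two months on the pill before enrollment, or three months on replacement before study entry, is longer than that. A woman who meets criterion 25 through the pill, or criterion 32, is therefore exposed at V1 and is expected to remain so.

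**2. What can the menses row show?**
- On a steroid and regular at V1: she cannot move from No to Yes, and a drug effect on her own cycle, good or bad, is hidden.
- On a steroid and not regular at V1: she can move, but the steroid is a competing explanation.
- Off steroids and regular at V1: she cannot move to Yes either. This has nothing to do with steroids.
- Off steroids and not regular at V1: this is the only group in which a No-to-Yes change can be read as a possible drug effect.

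Table 10 gives Improved as Yes, No and Total. It has no rule that removes any of the first three groups from the denominator.

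**3. What can the hormone rows show?** A stable pill can raise the abnormal LH, FSH and estradiol counts at every visit. A woman on replacement can have a normal estradiol although her own axis is deficient. The count at a given visit can therefore be too high or too low as a measure of gonadal dysfunction. A stable steroid does not by itself create a change from V1.

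**4. Can improvement be false?** Only if a steroid is started or changed after V1. Protocol 6.4.3 discourages this with an "if possible" condition and does not prohibit it.

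**5. What do the safeguards cover?** Table 31 covers replacement at V1 for estradiol (with testosterone, TSH and free T4). It does not cover menses, LH, FSH, the pill or any visit after V1, and a drug effect is read at the later visits. Table 4 is not linked to any outcome.

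**6. Illustration under assumptions.** Let r be the improvement rate among non-users and f the share of scored women on a steroid. Assume that users cannot change category and stay in the denominator. The reported rate is then r × (1 − f). For r = 40%:
- f = 25%: 0.40 × 0.75 = 30%
- f = 50%: 0.40 × 0.50 = 20%
- f = 75%: 0.40 × 0.25 = 10%

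For false improvement, assume 8 scored women, of whom 2 become regular after an on-study steroid change and none because of the drug. The table would show 2/8 = 25%, with an exact 95% CI of 3% to 65%. Neither f nor the number of women is in the documents.

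**The case against.** The strongest reply is that the plan is not blind to the issue. Table 31 separates replacement users at V1, and SAP section 7 lists the comparative hormone analysis as a deliberate clarification. Abnormal values are split into clinically significant and not, so a value expected on a steroid can be put in the second class. The entry rules fix the steroid before baseline. These are secondary, descriptive rows in a proof-of-concept study of 23 patients.

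Most of this stands as a limit on the concern, and it rules out several stronger readings that a reader might infer:
- *Error of equal weight in both directions.* A pill taken as criterion 25 requires cannot turn No at V1 into Yes by being started later. Masking is the main effect.
- *The pill explains hormone changes from V1.* It is present at V1 and afterwards. It affects the level at each visit, not by itself the change.
- *A fixed ceiling on improvement, such as 50%.* That needs an assumed share of users, all regular at V1. Women who are regular at V1 without steroids cannot improve either, so the ceiling is not only a steroid problem.
- *All the scored women must take sex steroids.* The pill is optional beside the diaphragm. Replacement is required only in confirmed hypogonadism.

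The reply does not remove the gap. Table 31 stops at V1 and omits menses, LH, FSH and the pill. The significance classes carry no stated rule about steroid use. Perfect stability of medication leaves the masking untouched.

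**Conclusion.** The concern holds in this limited form. The pooled rows cannot separate a pasireotide effect on menses or the gonadal axis from the effect of a steroid that the entry criteria allow or, in confirmed hypogonadism, require. The main consequence is a masked effect on menses and abnormal counts that are hard to interpret at each visit. Spurious improvement is possible but depends on an on-study steroid start or change.

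The size cannot be derived, because the number of non-menopausal women and the share on steroids are not given. The percentages in the working are illustrations only. The conclusion rests on the assumption that bleeding and gonadal hormones in users largely follow the steroid. The primary tumor-volume endpoint is not affected.

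A reader might also infer that users should simply be left out. The documents argue against that. Criterion 32 makes replacement the route of entry for women with confirmed hypogonadism, so dropping them would understate gonadal dysfunction. Dropping women who start a steroid later would condition on a post-baseline event and could hide a worsening.

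**What to change.** Change SAP 5.5.1 and Tables 10, B 5, 30 and B 23 as follows:
- Show menses, LH, FSH and estradiol separately for women on and off sex steroids (pill or replacement) at V1.
- Name menses improvement among women off sex steroids and not regular at V1 as the interpretable result.
- Count a woman who starts or changes a sex steroid on study as not improved from that visit on, and list her; do not remove her.
- In the incidence of pituitary hormone dysfunction, keep women on replacement for confirmed hypogonadism counted as having gonadal dysfunction, whatever their measured values.

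The cost is SAP wording and one derived flag. Prior and concurrent medication is already collected at V1 and through the main-phase and extension dosing visits (Protocol Tables 7-1 and 7-2) and coded by ATC class (Protocol 9.3). No new data and no change to patient care are needed.

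The downside is small strata. If there were 8 scored women (an assumption) and 4 were off steroids, a result of no improvement would have an exact 95% upper limit of 60% with 0/4, against 37% with 0/8 pooled. The wider interval reflects how few women are informative.

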#### 6 Treatment

# 6.1 Investigational drug

The study drug is pasireotide LAR (long-acting release), depot IM injection.

Pasireotide LAR excipients include: mannitol, sodium carmellose (sodium carboxymethyl cellulose), poloxamer 188, and water for injection.

#### 6.1.1 Known untoward effects of the study drug / treatment

Refer to the Investigator's Brochure for further information.

#### **6.1.2** Supply

Novartis will provide the investigational drug pasireotide LAR, as 20 and 40 mg of powder in vials and 2 mL of vehicle in ampoules (for reconstitution), provided in boxes.

The medication labels will meet the Brazilian legal requirements and will be printed in Portuguese. They will not contain patient information. The storage conditions of the study drug will be described in the medication label.

#### 6.1.3 Preparation and storage

Pasireotide LAR must be prepared as described on Table 6-1:

Table 6-1 Handling and preparation of pasireotide LAR dose

Dose (mg)	Volume to be injected
60 mg	1 20 mg vial + 1 40 mg vial + 2 mL of vehicle; total volume to be injected
40 mg	1 40 mg vial + 2 mL of vehicle: total volume to be injected

The doses must be prepared and administered immediately after preparation. For additional instructions on the handling and preparation of pasireotide LAR doses, refer to [Post-Text Supplement 3].

The drug supplies must be kept in an appropriate and safe area (for example, a locked cabinet) and stored according to the conditions specified on the drug labels. The receipt and dispensing of the study drug must be recorded by an authorized person at the Investigator's site. The Investigator must keep an accurate shipment and dispensing record of the study drug in a drug accountability log, and a copy of this form will be provided to Novartis at the end of the study. An accurate record of the date and amount of study drug dispensed to each subject must be available for inspection at any time. Unless specifically instructed by Novartis, the Investigator must not destroy the labels of any drug or any partially used and unused drug supply. Any partially used ampoule must not be reused in another injection.

# 6.2 Patient numbering

Each study patient is uniquely identified by a 6-digit patient number, which is a combination of the 3-digit site number and the 3-digit subject number. The site number is assigned by Novartis to the investigational site. Upon signature of the Informed Consent Form, the investigator or his/her designee assigns a number to the subject. Once assigned to a patient, the number will not be reused. If the patient cannot start treatment for any reason, this reason will be entered in the Screening Record electronic Case Report Form (eCRF), and the patient's demographics will be entered in the Demographics eCRF.

The Informed Consent Form must be obtained before performing any test to determine the patient's eligibility.

# 6.3 Treatment assignment

This is a single-arm open-label study. All patients will receive pasireotide LAR 60 mg every  $28 \pm 3$  days for 24 weeks. In case of problems related to drug tolerability, the treatment dose may be adjusted (see Section 6.6.2) or the study medication may be discontinued (see Section 6.4.2).

